4.4.5.2.2 Overall Survival

OS is defined as the time between the date of first treatment and the date of death due to any cause. Subjects who are alive or have the competing events of "definite" loss to follow-up or withdrawal of consent will be right censored at the date of last contact.

OS = Date of death/competing event/censoring - date of first treatment + 1.

Imputation of missing date parts will follow the rules previously specified. Competing events for death are “definite” lost to follow-up and withdrawal of consent for continued vital status assessments. Both competing events are subject to revision for an individual subject with the passage of time. Subjects will be censored for competing events as well as survival by using their last contact date in the clinical database.

The 12-month OS rate and the product-limit estimate of median survival, as well as their 90% confidence intervals will be summarized. A Kaplan-Meier curve will summarize OS graphically. The 18-month and 24-month survival rates will also be provided along with their 90% CIs.

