### 4.2.3 Long Term Follow-up Period

During the Long-Term follow-up (LTFU) period, subjects will be followed by phone contact at quarterly intervals for survival status assessment and potential autoimmune or immune-mediated clinical manifestations. The FU period may be extended up to 2 years.

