#### **4.2.5.2 Discontinuation from Long Term Follow-up**

All subjects will be followed until death, via telephone contacts at 3 month intervals, to evaluate OS unless the trial is suspended or discontinued. The length of the LTFU is planned to be 2 years, unless all subjects achieve their OS endpoint prior to the end of the 2-year period. If a subject chooses to withdraw from trial survival follow-up, this request must be documented in the source documentation and signed by the investigator. If the subject withdraws from participation in long term telephone follow-up, the trial staff may use a public information source (such as county records) to obtain information about survival status only.

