### **Missing Data**

For duration of OS, PFS, or duration of response, subjects who are lost to FU will be analyzed as censored observations on the date of last known alive for OS, or last radiographic assessment for PFS and duration of response. Missing or partial dates will be imputed for prior/concomitant medications, adverse events, and cancer history. Details will be provided in the statistical analysis plan.

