4.3.2 Missing or Partial Dates

All data will be listed and summarized as captured in the electronic Case Report Form (eCRF) or transferred from external sources (e.g., lab, ECG). It may be necessary to impute incomplete dates to correctly assign events to a period or to calculate durations.

For prior and concomitant medications, AEs, and cancer history dates the following rules will apply:

Missing	Rule for start date	Rule for end date	Flag for imputation
Day	First of month	Last of month*	D
Month [†]	1 January	31 December*	M
Year [†]	First Treatment Date	Date of Data Cutoff/Lock	Y

* Unless the imputed start date is before first visit date, in which case first visit date is used; or the imputed stop date is after last visit date in which case last visit date available is used.

† It is assumed that a missing Month implies a missing Day as well, and that a missing Year implies a missing Month and Day.

If the imputation of an AE start date leads to a date prior to the date of first vaccination, and it is possible that the AE start date can be on or after date of first vaccination based on partial date information (e.g., occurred on the same month), it will be set to the date of first vaccination to be conservative. In the event the imputation of an end date leads to a date after the death date of a subject, the death date will replace the imputed date.

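### SAP 4.4.5.2.2 applies the medication, adverse-event and cancer-history date rules to partial death dates, and those rules misdate deaths by an amount and direction that depend on how they are read

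*SAP*

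**What the plan says.** SAP 4.4.5.2.2 computes OS as death or censoring date minus first-treatment date plus 1, so any change in the death date passes day for day into OS. For incomplete dates it says only: "Imputation of missing date parts will follow the rules previously specified". Subjects not known to have died are censored at their last contact date.

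The only earlier rules are in SAP 4.3.2, introduced with "For prior and concomitant medications, AEs, and cancer history dates the following rules will apply". The Missing Data paragraph of the Protocol has the same scope: "Missing or partial dates will be imputed for prior/concomitant medications, adverse events, and cancer history". Death is in neither list.

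The 4.3.2 table has two columns:

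- **Start date:** first of the month, 1 January, or the first treatment date when day, month or year is missing.
- **End date:** last of the month, 31 December, or "Date of Data Cutoff/Lock".

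A footnote raises a start date that precedes the first visit to that visit. It also caps the day-missing and month-missing end dates: "or the imputed stop date is after last visit date in which case last visit date available is used". The year-missing end date carries no cap. Finally, where an imputed end date "leads to a date after the death date of a subject, the death date will replace the imputed date".

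After treatment, Protocol 4.2.3 provides that "subjects will be followed by phone contact at quarterly intervals for survival status assessment". For subjects who withdraw from that telephone follow-up, Protocol 4.2.5.2 adds that "the trial staff may use a public information source (such as county records) to obtain information about survival status only".

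**The concern.** Section 4.3.2 is unsuitable for deaths in three ways. It does not say whether a death is a start or an end date. It uses the death date as a known limit on other dates, so using it to derive that date is circular. And neither column keeps the imputed death on or after the last date known alive. A subject reached alive by phone can therefore be recorded as dead before the call, although the same OS section censors living subjects at last contact.

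What is at stake is the median OS and the 12-, 18- and 24-month OS rates, all named secondary results. Deaths learned of by phone or from public records are the ones most likely to lack a day or month. The trial is open-label and single-arm (SAP 2.2.2), so if the column and the meaning of the cap are settled at programming, they are settled with outcomes visible. Death is also an event in progression-free survival (PFS) and duration of response.

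**Working it through.** The plan states no figure here, so there is none to reproduce. I applied the 4.3.2 table and footnote literally to example deaths.

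**Assumed dates:** first treatment 4 March 2019, cutoff 31 December 2022. End-of-treatment (EOT) visits in cases A and B are 28 days after the scan showing progression (Day 64 and Day 148), the limit in Protocol 1.5, footnote 12. Follow-up contacts are roughly quarterly.

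OS in days, with the error in brackets:

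| Case: last clinic visit / last contact / true death | Part missing | Start column | End column, cap = clinic visit | End column, cap = contact |
|---|---|---|---|---|
| A: 92 / 274 / 330 | day | 304 (-26) | 92 (-238) | 274 (-56) |
| A | month | 304 (-26) | 92 (-238) | 274 (-56) |
| B: 176 / 359 / 400 | day | 395 (-5) | 176 (-224) | 359 (-41) |
| B | month | 304 (-96) | 176 (-224) | 359 (-41) |
| C: 694 / 968 / 1000 | day | 974 (-26) | 694 (-306) | 968 (-32) |
| C | month | 670 (-330) | 694 (-306) | 968 (-32) |
| D: 274 / 274 / 284 | day | 273 (-11) | 274 (-10) | 274 (-10) |

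At 30.4375 days per month, the clinic-visit errors in A to C are -7.8, -7.4 and -10.1 months.

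**Year missing.** The start column gives first treatment minus first treatment plus 1 = 1 day in every case. The end column gives the cutoff, Day 1399, so OS is too long by 1069, 999, 399 and 1115 days in A to D.

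**Deaths dated before a time the subject was known alive.**

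- B, month missing, start column: Day 304, before the Day 359 contact.
- C, month missing, start column: Day 670, before the Day 694 visit.
- D, day missing, start column: Day 273, before the Day 274 visit.
- A to C, end column with the clinic-visit cap: each death precedes a later phone contact.

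**Typical size under the end column.** For a death after the last visit, the last day of that month and 31 December of that year both fall on or after the death. The cap therefore always applies, and the error equals the time from last visit to death. Take exponential survival with rate λ = ln 2 / median, and deaths within the 24 months of long-term follow-up. The median error is

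-ln[1 - 0.5(1 - e^(-24λ))] / λ.

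The OS medians come from the atezolizumab studies in Protocol 2.1 and are used only for sizing:

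- 8.6 months: λ = 0.0806, median error 6.9 months (mean 8.4).
- 11.4 months: λ = 0.0608, median error 8.0 months (mean 9.2).
- 15.9 months: λ = 0.0436, median error 9.0 months (mean about 10).

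If the cap is the last quarterly contact before death, the mean error is 1.4 to 1.5 months, and about 3 months at most. The exponential shape is rough: at a 15.9-month median it implies 12-month OS of 2^(-12/15.9) = 59%, where Protocol 2.1 reports 75%.

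**Effect of one death crossing a landmark:** 1/33 = 3.0 points, 1/35 = 2.9 points. In a cohort stopped at Stage 1: 1/14 = 7.1 points, 1/13 = 7.7 points.

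**The case against.** The strongest reply is that this is a drafting gap with a modest effect on any sensible reading. Several parts of it stand.

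- **Death is never called a stop date.** Under the start column a missing day costs at most 30 days.
- **The cap need not be the last clinic visit.** The SAP definition of long-term follow-up separates visit from contact, but it also speaks of follow-up visits, as does SAP 4.3.1. Protocol 8.2.5 calls the remote follow-up a visit. If the contact that reports the death counts, it comes after the death and the cap does not shorten OS.
- **The error is not always downward.** A missing year in the end column lengthens OS.
- **OS is descriptive.** No test depends on it, and published rates set only the null response rates.
- **The reach into PFS and duration of response is limited.** The cross-reference sits in the OS section, and a death after progression changes neither endpoint.

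A reader might therefore infer too much: that the plan moves every partially dated follow-up death back to the last clinic visit and shortens OS by months. The documents do not fix that reading. A reader might also infer that deaths will be dated before treatment began. The 4.3.2 footnote raises such dates to the first visit. If that is Visit 1 the problem cannot arise, and if it is screening the gap is limited to a nominal 28 days.

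The reply does not supply a valid rule. No reading of 4.3.2 sets a floor at the last date known alive, and the readings disagree widely on the same partial date.

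**Conclusion.** The point holds in this form: the SAP directs partial death dates to rules that were not built for them and that misdate deaths under either column. The direction and size depend on the reading. Across the follow-up examples, the same death can give OS anywhere from 1 day to the data cutoff, according to which part is missing and which column is used. With only the day missing, the error runs from a few days to about 10 months.

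The 7-to-9-month figure requires three things together: the end-date column, a cap at the last clinic visit, and roughly exponential survival at the medians cited in the Protocol. If follow-up contacts count as visits, it falls to about 1.5 months.

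The effect on a reported OS rate cannot be predicted, because the documents give no expected number of partial death dates. Each death that crosses a landmark is worth about 3 points at full enrollment. The primary response-rate analysis and its error rates are untouched. The text should be corrected before OS is programmed, but the point does not threaten the trial's main conclusion.

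**What to change.** Replace the cross-reference in SAP 4.4.5.2.2 with a rule for death dates:

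- Apply no last-visit cap.
- Never date the death before the last date known alive.
- Never date it after the date the death was reported, or after data cutoff if the report date is not recorded.
- Day missing: for example the 15th of the known month, moved to the nearer bound if it falls outside them.
- Month or whole date missing: for example the midpoint of the bounds, narrowed to the known year where there is one.
- Use the same date wherever death is the PFS or duration-of-response event.

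The 15th and the midpoint are conventions. The two bounds are what matters. With the day missing, the mid-month rule with the lower bound gives OS of 318, 409, 988 and 287 days in cases A to D, errors of -12, +9, -12 and +3 days. The report-date bound could only pull these earlier.

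The cost is a few lines of SAP text and code. The last contact date is already used for censoring. The documents do not say whether the date a death was reported is captured, hence the fallback to data cutoff.

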4.4.5.2.3 Duration of Response

Duration of response is defined as the time from response (CR or PR, whichever occurs first) to investigator assessed progression using RECIST v1.1 or death, and will be summarized based on the number of subjects with response in the FAS. Subjects who do not have disease progression or have not died will be censored at the date when the last tumor assessment determines a lack of progression.

Duration of response will be summarized using the product-limit estimate of median survival along with its 90% confidence interval. The Kaplan-Meier curve will summarize duration of response graphically.

In case some additional immune-related responders are observed, duration of response analyses using iRECIST criteria will be provided. For subjects who are not evaluated by iRECIST criteria, their tumor response based on RECIST v1.1 response guidelines will be used.

4.4.6 Exploratory Endpoint Analysis

4.4.6.1 Tissue Biopsy Variables

Pre-treatment tumor tissue samples are required for inclusion in the trial, and will be collected at screening if an archived tumor sample is not available. Optional tumor biopsies will be collected at any of the following visits: Visit 3 through 6, but are not required.

- Number and localization (immunoscore) of Tumor-Infiltrating Lymphocytes
- Number and localization (immunoscore) of PD-L1 positive tumor cells (TPS) and immune cells.
- Presence and strength of gene expression signatures correlated to immune status and response (signatures ranked from low to high)

The following analyses will optionally be performed based on BN review of previous results:

- Diversity of T-cell receptor clonality – (higher number of specific clones is a better outcome)

- Degree of tumor mutational burden (burden ranked from low to high)
- Presence and degree of DNA damage response gene mutations (MSI status [positive/negative], MMR deficiency status [mutated/not mutated])

4.4.6.2 Peripheral Blood Mononuclear Cells and Serum

PBMC and serum samples will be taken at Screening, as well as visits 2, 4, 7, and 10.

PBMC Variables

- Number of specific spot forming units and/or antigen specific cells per 10^6 PBMC in stimulations with peptide pools of CEA, Mucin-1 or other Tumor-associated antigens
- Percentage of defined immune cell populations
- T-cell receptor clonality (see above)

Serum Variables

- Amount of soluble biomarkers including cytokines and classical tumor markers

4.4.6.3 Exploratory Endpoint Analysis

In general, analyses of exploratory endpoints will be based on the FAS with available data for the exploratory analyses. Missing data will not be imputed. Analyses will focus on comparing the post-baseline values with the baseline values for changes in the measured parameters of immune response.

Correlation between objective tumor response or clinical parameters and measured parameters of immune responses will be explored.

Continuous data will be summarized via mean (and 95% CI), standard deviation, median, minimum, and maximum by visit where samples are collected per trial schedule. In case of log-normal data, log transformations may be performed and summarized with the geometric means in place of the arithmetic means and 95% CIs.

Detailed analyses for the exploratory immune response measures will be added to a SAP amendment when preliminary results are available.

4.4.7 Disposition and Trial Population Information

4.4.7.1 Disposition

All subjects screened will be accounted for in a disposition table and CONSORT diagram (Schulz et al., 2010). A summary table will be presented specifying the number of subjects screened, treated, completing the active treatment phase, included in each analysis set,

withdrawing from active treatment phase, entering follow up, and the number withdrawing from follow up. For subjects withdrawing from treatment or follow up, the frequency of primary reasons for withdrawal will also be summarized. A separate summary for screening failures and reason for screening failure will also be presented.

A listing will present all screened subjects, date of completion or discontinuation, date of last dose of trial product, reason for discontinuation from treatment, and reason for withdrawal from follow up.

4.4.7.2 Analysis Populations

Frequencies and percentages of each trial population will be presented along with disposition. Reasons for exclusion from any population group will be included in the screening failure or protocol deviations summaries.

4.4.7.3 Protocol Deviations

Protocol deviations are collected on both a site and subject-level basis. Subject level deviations will be databased and listed, including deviation term, deviation category, and affected visits or dates. Categorized deviations will be summarized using frequencies and percentages in a table for the FAS.

4.4.7.4 Demographics and Baseline Characteristics

Variables

- Age at Screening (years)
- Age Group 1 (< 45, ≥ 45 – < 55, ≥ 55 – < 65, ≥ 65 – < 75, ≥ 75)
- Age Group 2 (< median, ≥ median)
- Sex (Male, Female)
- Childbearing Status (Yes, No: Post-Menopausal, No: Surgically Sterile, N/A)
- Race (White, Black or African American, Asian, Native Hawaiian or Other Pacific Islander, American Indian or Alaska Native, Other)
- Ethnicity (Hispanic or Latino, Not Hispanic or Latino)
- Height [cm]
- Body weight [kg]
- BMI [kg/m²]
- Tobacco Use (Current Smoker, Previous Smoker, Never Smoked)

Analyses

Subject-level listings will be presented for all data in the database. Tables of descriptive statistics for demographics will be produced for the FAS. Descriptive statistics will be presented for the continuous demographic variables by cohort and overall. Frequencies and percentage of subjects will be tabulated for all categorical variables by cohort and overall. Percentages will be based on the total number of subjects in the FAS for demographics and baseline disease characteristics within each cohort.

The following formula will be used to calculate BMI:

$$\text{BMI} = \text{Weight (kg)} / [\text{Height (m)}]^2$$

4.4.7.5 Bladder Cancer History and Baseline Disease Characteristics

Variables

- Eastern Cooperative Oncology Group (ECOG) Performance Status (0, 1, ≥ 2)
- Time from Initial Diagnosis to First Treatment (years)
- Duration of Primary Curative Intervention (months)
- Disease Free Interval (months)
- Time from Recurrence after a Disease-Free Interval to First Treatment (years)
- Primary Tumor Site (Renal Pelvis, Ureter, Urethra, Urinary Bladder, Other)
- Stage at Diagnosis (I, II, III, IV)
- T Category (T_x, T₀, T_a, T_{is}, T₁, T_{2a}, T_{2b}, T_{3a}, T_{3b}, T_{4a}, T_{4b})
- N Category (N_x, N₀, N₁, N₂, N₃)
- M Category (M₀, M₁)
- PD-L1 tumor proportion score (TPS; < 1%, $\geq 1\% - 10\%$, $\geq 10\%$)
- Current Metastatic Disease Sites (Yes, No)
 - Sites of Current Metastatic Disease: Adrenals, Bone, Bone Marrow, Chest Wall, Central Nervous System/Brain, Fallopian Tubes, Kidney, Large Intestine, Liver, Lung, Lymph Nodes, Pancreas, Peritoneum, Pleura, Rectum, Small Intestine, Spleen, Stomach, Uterus, Other

Analyses

Missing dates for cancer history will be imputed per Section 4.3.2. Frequencies and percentage of subjects will be tabulated for categorical variables by cohort and overall. Percentages will be

based on the total number of subjects in the FAS within each cohort. The following formulas will be used to calculate the above time-specific variables:

Time from Initial Diagnosis to First Treatment = (Date of First Treatment – Date of Initial Diagnosis + 1)/365.25

The following will be included only in subject-level listings:

Duration of primary curative intervention in months = (End Date of Primary Curative Intervention – Start Date of Primary Curative Intervention + 1)/30.4375

Disease-free interval in months = (Date of Recurrence – End Date of Primary Curative Intervention + 1)/30.4375

Time from Recurrence after a Disease-Free Interval to First Treatment in months = (Date of First Treatment – Date of Recurrence + 1)/30.4375

4.4.7.6 General Medical History and Baseline Signs and Symptoms

Medical history data are collected at screening and coded to MedDRA version 21.0 preferred terms (PTs) and system organ classes (SOCs). Summaries of medical history events will be created by PT and SOC for the FAS. SOCs will be sorted by descending incidence, and within each SOC, PTs will be sorted by descending incidence in the overall column.

Baseline signs and symptoms are defined as AEs that occur between the signing of informed consent and the first treatment with trial product. These events are to be reported along with the TEAEs in the CRF, but will be summarized separately as events prior to the initiation of treatment with trial product. Like medical history events, they will be coded to MedDRA PTs and SOCs. Baseline signs and symptoms will also be listed by SOC and PT along with the AE data. Relative day of onset will be calculated as described in Section 4.3.5.

4.4.7.7 Prior and Concomitant Medication and Procedures

All prior and concomitant medication will be coded to WHO DDE (B3 version 2018 Mar) Anatomic-Therapeutic-Chemical (ATC) classes and preferred names. Displays of **prior** medications include medications where end date is before date of first administration of trial product. Displays of **concomitant** medications include all medications started prior to first treatment and are ongoing, medications with missing end dates, or medications with start dates after the first administration of trial product. Tables by ATC class and preferred name, ordered in descending incidence of ATC class and preferred name within ATC class, will be presented for the FAS. Subject level listings will be created based on the original CRF data along with the WHO Drug coding results.

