### **8.2.2.2 Prohibited Medications**

The following medications are prohibited during the trial, as well as prior to Day 1 based on the relative type of medication. Additional medications may be deemed prohibited based on review during screening, if there is the risk to the subject or the ability to capture the trial outcome for the subject.

- Any approved or experimental anti-cancer therapy including chemotherapy within 3 weeks prior to Day 1, and throughout the trial.
- Treatment with any other investigational agent within 28 days prior to Day 1.
- Therapeutic oral or IV antibiotics within 1 week prior to Day 1.
- Live, attenuated vaccine including influenza vaccine (FluMist), within 4 weeks of Day 1 and throughout the trial.
- Prior treatment with CD137 agonists or immune checkpoint blockade therapies, including anti-CTLA-4, anti-PD-1 and anti-PD-L1 therapeutic antibodies and throughout the trial.
- Treatment with systemic corticosteroids or other systemic immunosuppressive medications (including but not limited to prednisone, dexamethasone, cyclophosphamide, azathioprine, methotrexate, and anti-TNF agents) within 2 weeks prior to Day 1 and throughout the trial, or anticipated requirements for systemic immunosuppressive medications during the trial.

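### The SAP's date rules place a medication that starts on the day of first dosing and has a recorded end date in neither the prior nor the concomitant summary table

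*SAP*

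**What the plan says.** SAP 4.4.7.7 gives the only date-based split of medications in either document. The prior display takes "medications where end date is before date of first administration of trial product". The concomitant display is to "include all medications started prior to first treatment and are ongoing, medications with missing end dates, or medications with start dates after the first administration". That gives three routes into the concomitant display:

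1. a start before first dosing, and ongoing;
2. no end date, whatever the start;
3. a start later than first dosing.

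The tables are by ATC class and preferred name for the FAS. Listings follow a different rule: "Subject level listings will be created based on the original CRF data along with the WHO Drug coding results". Protocol 9.6 promises an incidence summary of prior and concomitant use in the FAS but sets no date boundary between the two.

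Three other SAP provisions bear on the point:

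- Section 4.3.2 covers incomplete medication dates. A start date with missing year becomes the date of first treatment.
- The General Definitions count trial days by calendar date and ignore the clock time of vaccination.
- For adverse events the same day is covered. The treatment-emergent definition includes onset on the day trial product is started, and section 4.3.4 assigns an event falling on a vaccination date to the period of that vaccination.

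**The concern.** The prior and concomitant rules should together cover every recorded medication. As written they leave a gap of one calendar day. The prior rule needs an end date strictly before first dosing, and routes 1 and 3 of the concomitant rule need a start date strictly before or strictly after it. A start date equal to the dosing date qualifies only through route 2.

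Day 1 is the day of the first prime vaccination and the first atezolizumab infusion. A short course begun that day is foreseeable: Protocol 8.2.2.1 permits acute low-dose systemic corticosteroids and gives a one-time dose of dexamethasone as an example. Followed literally, the SAP would tabulate an adverse event with onset on Day 1 but could leave out the one-day drug given for it. What is at stake is the completeness of a descriptive table, not an inference.

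**Working it through.** The plan states no figure here, so the check is one of date logic. Let D be the date of first administration (Day 1), s the start date and e the end date.

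- Prior: e < D.
- Concomitant: (s < D and ongoing), or e missing, or s > D.

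Take s = D with a recorded end date, so e ≥ D. Prior fails because e is not before D. Route 1 fails because s is not before D. Route 2 fails because e is recorded. Route 3 fails because s is not after D. The record is in neither table.

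Eight start/end patterns were classified. The word ongoing was read in two ways: (a) still being taken at first dose, and (b) no end date in the database.

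| Start | End | Prior | Concomitant, reading (a) | Concomitant, reading (b) | Concomitant after the fix |
|---|---|---|---|---|---|
| Day −5 | Day −2 | yes | no | no | no |
| Day −5 | Day 1 | no | yes | no | yes |
| Day −5 | Day 10 | no | yes | no | yes |
| Day −5 | none | no | yes | yes | yes |
| **Day 1** | **Day 1** | **no** | **no** | **no** | **yes** |
| **Day 1** | **Day 5** | **no** | **no** | **no** | **yes** |
| Day 1 | none | no | yes | yes | yes |
| Day 2 | Day 2 | no | yes | yes | yes |

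The two rows in bold are lost under either reading. A Day 1 start without an end date is kept through route 2.

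Imputation: if the year of the start date is missing, section 4.3.2 sets s = D. With a known end date on or after D, the record then behaves like the bold rows, whatever its true start.

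Size per subject: the tables show incidence, so a subject drops out of a drug's row only if no other record of that drug qualifies. Each such subject lowers the row by 1/n. At the sizes in SAP 4.1:

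- Cohort 1: 1/33 = 3.0 percentage points at full size, or 1/14 = 7.1 if stopped after Stage 1.
- Cohort 2: 1/35 = 2.9 points at full size, or 1/13 = 7.7 if stopped after Stage 1.

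The number of subjects affected cannot be derived from the documents and could be zero.

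**The case against.** The best defence is that this is two missing words in a descriptive-table rule, that a programmer would notice records falling in no category, and that nothing is lost from the data. Much of that stands. The listings come from the original CRF data, Day 1 reactions are still counted as adverse events, and no endpoint, analysis set, censoring rule or error rate uses this split. It does not remove the gap: the Introduction of the SAP says that the plan will be followed completely, and the rule as written is incomplete.

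A clock-time defence is also possible. A drug given after the infusion on Day 1 starts, in the ordinary sense, after the first administration. But route 3 compares start dates, the SAP gives no time-of-day rule for medications, and its trial-day convention ignores clock time.

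A reader might infer more than the documents support:

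- *Every drug started on Day 1 is left out.* No: a Day 1 start with a missing end date is concomitant through route 2.
- *Drugs started before Day 1 and stopped during the trial are lost as well.* Only under reading (b), which is strained because it would make route 1 largely repeat route 2. Reading (a) is the natural one and keeps them.
- *Day 1 premedication and infusion-reaction treatment are systematically lost.* The protocol's visit description and its atezolizumab section name no such Day 1 drugs; how often they would be given is an assumption.
- *Monitoring of restricted immunosuppressants is compromised.* Protocol 8.2.2.2 restricts "Treatment with systemic corticosteroids or other systemic immunosuppressive medications", but neither document makes the concomitant table the measure of that exposure. SAP 4.4.7.3 plans a separate table of categorised protocol deviations for the FAS.

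**Conclusion.** The point holds in a narrow form. Under SAP 4.4.7.7 as written, a medication whose start date is the date of first administration, recorded or imputed, and which has a recorded end date appears in neither summary table. The contrast with the same-day rules for adverse events suggests an oversight rather than a choice.

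The consequence is minor: an understated incidence in some rows of a descriptive table, limited to subjects with no later use of the same drug. ATC class rows are affected less, since any other qualifying drug of the class keeps the subject in the count. Listings and efficacy results are unaffected.

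The conclusion rests on two assumptions: that dates are compared by calendar day, and that a missing end date is judged on the recorded value before imputation. No count of affected subjects is offered, because the documents give no frequency for Day 1 medication.

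**What to change.** In SAP 4.4.7.7, define a concomitant medication as one with an end date on or after the date of first administration of trial product, or with a missing end date or recorded as ongoing, regardless of start date. Leave the prior definition unchanged.

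The two definitions are then complements: a recorded end date is either before D or not, and a missing one counts as concomitant. Every record falls in exactly one display, as the last column of the table shows. Because the start date no longer enters the rule, the new wording also settles the meaning of ongoing and makes the imputed start date irrelevant to the split.

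The cost is one sentence in the SAP and one line of derivation code. No additional data are needed, and nothing else in the plan changes.
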